**Post Myocardial Infarction Risk Stratification for Sudden Cardiac Death in Patients
with Preserved Ejection Fraction (PRESERVE EF) Study**

Clinicaltrials.gov identifier: NCT02124018

January 23rd 2019

Methods

Trial oversight: The PRESERVE EF study is a multicenter, prospective, observational cohort study (clinicaltrials.gov identifier NCT02124018) with seven Cardiology departments in Greece actively participating. Study protocol was approved by all institutions' ethics committees and was endorsed by the Hellenic Society of Cardiology with an anonymized online database created and maintained in its servers(1).

Patients: Post-angiographically proven MI patients, at least 40 days after the event (90 days after surgery if they underwent coronary artery bypass grafting)(2, 3), with LVEF \geq 40% (also assessed after 40 or 90 days, respectively from the index event), either revascularized or not – but without any evidence of active ischemia (following negative myocardial scintigraphy/exercise treadmill test/stress echocardiography in the previous 6 months), on optimal tolerated medical therapy, were enrolled. Exclusion criteria were: (1) Presence of a secondary prevention indication for ICD implantation, (2) Presence of a permanent pacemaker, due to potential effects on NIRF acquisition following pacemaker dependency and cardiac memory(4), (3) Persistent, long-standing persistent and permanent atrial fibrillation, (4) Neurological symptoms (presyncope or syncope) within the last 6 months, (5) Patients with systemic illnesses (cancer, liver failure, end-stage renal disease, rheumatic diseases and thyroid dysfunction), (6) Administration of antiarrhythmic medication other than β -blockers, (7) Age \geq 80 or \leq 18 years old.

All patients provided written informed consent.

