Patients declining PVS were considered not to have completed stratification and were not included in the protocol performance and survival analyses, yet were followed up as scheduled for the occurrence of any events. Patients completing the protocol but declining an offered ICD were fully included in all analyses.

ICD programming: In accordance with trials favouring prolonged detection intervals at higher rates for the avoidance of treatment of self-terminating arrhythmic events(9), ventricular tachycardia therapy cycle length was set to 330msec and number of intervals to detect to 32. Fibrillation therapy cycle length was set to 270msec and number of intervals to detect to 18/24. In devices with time programming, the same cycle lengths were used but intervals were set to 7sec for CLs in the 270-330msec range and to 2.5sec for CLs<270msec.

Ventricular tachycardia therapy consisted of several attempts of antitachycardia pacing, followed by cardioversion at progressively increasing energy. High-energy shocks were administered to terminate ventricular fibrillation. In 32 cases dual-chamber ICDs were inserted, while in the remaining 5 a single-chamber device was chosen by both the primary and implanting physicians, after excluding the presence of bradyarrhythmic aberration on the electrophysiological study.

Follow up: Implanted patients were followed up every three months, and nonimplanted patients every six months. Events included cardiac (sudden and nonsudden) and non-cardiac death. Acute coronary syndromes and/or repeat revascularization events were also recorded. All device activation were adjudicated independently by two electrophysiologists ([name] and [name]). In case of discrepancy, a third electrophysiologist ([name]) reviewed the event.

Outcomes: The primary endpoint of the study was the occurrence of MAEs, namely either SCD/clinical ventricular tachycardia/fibrillation or/and appropriate ICD activation. SCD was defined as death occurring within one hour of symptom onset if no evidence of alternative causes was present. Death was considered nonsudden cardiac if occurring in the context of heart failure deterioration. All other deaths were classified as noncardiac. The secondary endpoint was total mortality.

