Statistics: The primary goal of the study was to assess the proposed two-step PVS-inclusive risk stratification algorithm's ability to identify a subpopulation of post-myocardial infarction patients with left ventricular ejection fraction $\geq 40\%$ at risk for MAEs. To that end, the study was designed to have a statistical power of 80% for detecting free from primary endpoint occurrence survival curve divergence at the 0.05 significance level(1). All continuous variables were checked for normality of distribution, using the Shapiro-Wilk test. Regarding those with normal distribution, Student's t-test was used for all comparisons. In case of non-normality, the Mann-Whitney U-test was used. In cases of categorical variables Fisher's exact test was used. Binary logistic regression was used to compare the odds ratio between groups with different number of NIRFs regarding inducibility. Kaplan-Meier curves were used to visualize survival free from primary endpoint occurrence and the logrank test was applied to assess the presence of statistically significant differences. A two-sided p-value of ≤ 0.05 was considered statistically significant in all cases.

Power analysis(1): Due to the paucity of data regarding PVS yield in similar population cohorts, it was necessary to use metrics derived from noninvasive indices included in this Study as well. After setting the type I error probability for a two sided test at 5% and the power of our study at 80%, SDNN was found to be the variable that required the largest sample (a ratio of high SDNN patients/controls to low SDNN patients/exposed equal to 12 was anticipated). The anticipated accrual/mean follow up intervals were 2 and 3 years, respectively. Relative risk (based on SDNN performance) of control subjects relative to exposed subjects was equal to 0.65. Based on the above, 66 exposed subjects and 792 control subjects would need to be studied to be able to reject with a probability of 80% the null hypothesis that the exposed and control survival curves are equal.

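### Kaplan-Meier display of MAE-free survival, with no competing-risk method for other deaths, slightly overstates absolute MAE risk; the logrank comparison is unaffected

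*Combined protocol and SAP*

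**What the plan says.** The Outcomes paragraph defines the endpoint: "The primary endpoint of the study was the occurrence of MAEs, namely either SCD/clinical ventricular tachycardia/fibrillation or/and appropriate ICD activation". Deaths outside that definition are collected and classified. Under Follow up, "Events included cardiac (sudden and nonsudden) and non-cardiac death". Under Outcomes, "Death was considered nonsudden cardiac if occurring in the context of heart failure deterioration" and "All other deaths were classified as noncardiac". These deaths enter the analysis only through a separate endpoint: "The secondary endpoint was total mortality".

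For the primary endpoint, the Statistics section says that "Kaplan-Meier curves were used to visualize survival free from primary endpoint occurrence" and that "the logrank test was applied to assess the presence of statistically significant differences". It states no censoring rule and does not mention cumulative incidence or any other competing-risk method.

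**The concern.** A patient who dies of heart failure or a noncardiac cause can no longer have an MAE. A Kaplan-Meier curve for an endpoint that excludes such deaths has to remove those patients as censored. It then treats them as if their later MAE risk were the same as that of the patients still under observation. One minus the curve estimates the MAE risk in a hypothetical setting without other deaths, under independence. It does not estimate the proportion of the group that will have an MAE.

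What is at stake is the absolute risk that a reader takes from the figure. The study asks whether the algorithm picks out patients at risk for MAEs, and Group 3 is the only group offered an ICD, so readers are likely to read a 3-year risk off its curve.

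**Working it through.** **Is there a figure in the plan to reproduce?** No. The documents give no absolute MAE risk, MAE rate or death rate. The Power analysis figure (66 + 792 = 858) rests on the SDNN relative risk, the 12:1 ratio, and the alpha, power and follow-up settings. None of these depends on how the curves are drawn.

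**Direction.** Let m be the MAE hazard and d the hazard of non-MAE death. In each short interval, one minus Kaplan-Meier adds m times the probability of being MAE-free, ignoring other deaths. The cumulative incidence adds m times the probability of being both alive and MAE-free. The first probability is never smaller than the second, so one minus Kaplan-Meier is at least as large as the cumulative incidence. They are equal if there are no non-MAE deaths.

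**Size.** Inputs:
- Horizon t = 3 years, the anticipated mean follow-up in the Power analysis.
- m = 5% or 10% per year and d = 1%, 2% or 5% per year. All of these are assumptions.
- Constant hazards, also an assumption.

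Formulas:
- One minus Kaplan-Meier = 1 − exp(−mt)
- Cumulative incidence = m/(m+d) × [1 − exp(−(m+d)t)]

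Example with m = 0.10 and d = 0.02: 1 − exp(−0.30) = 25.92%, and (0.10/0.12) × [1 − exp(−0.36)] = 25.19%. The difference is 0.72 points before rounding.

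| MAE rate per year | Other-death rate per year | 1 − KM, 3 years | Cumulative incidence, 3 years | Excess, points | Excess, relative |
|---|---|---|---|---|---|
| 5% | 1% | 13.9% | 13.7% | 0.2 | 1.5% |
| 5% | 2% | 13.9% | 13.5% | 0.4 | 3.0% |
| 5% | 5% | 13.9% | 13.0% | 1.0 | 7.5% |
| 10% | 1% | 25.9% | 25.6% | 0.4 | 1.4% |
| 10% | 2% | 25.9% | 25.2% | 0.7 | 2.9% |
| 10% | 5% | 25.9% | 24.2% | 1.8 | 7.3% |

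At lower MAE rates the excess in points is smaller. With MAE 2% and other deaths 1-2% per year, one minus Kaplan-Meier is 5.82% against 5.74% and 5.65%, an excess of 0.09 to 0.17 points. The excess grows with the horizon. With MAE 10% and other deaths 2% per year, it is 1.75 points at 5 years (39.35% against 37.60%).

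**Against sampling error.** ICD programming reports 32 + 5 = 37 devices, and ICDs were offered only to Group 3. Patients who declined stay in the analysis, so Group 3 has at least about 37 patients; its exact size is not stated. Taking n = 37 and ignoring censoring, the binomial standard error is:
- at 25.9%: √(0.259 × 0.741 / 37) = 7.2 points
- at 13.9%: √(0.139 × 0.861 / 37) = 5.7 points

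The largest excess in the table is 1.76/7.2, about a quarter of one standard error. The smallest is 0.2/5.7, about 4% of one.

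**The logrank test.** At each MAE time, the test compares observed with expected MAEs among patients still alive, MAE-free and under follow-up. A patient who has died of another cause is rightly absent from that risk set. The test therefore remains a valid comparison of cause-specific MAE hazards, provided that the remaining censoring is noninformative.

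**The case against.** The strongest case against the point is that the planned inference does not use absolute risk at all. The Statistics section ties the primary goal to divergence of the event-free curves at the 0.05 level, tested by logrank, and Kaplan-Meier is there only for display. The bias is a small fraction of a standard error in Group 3. The upper figures need 5% other deaths per year, which has no source in the documents. It also sits uneasily with the Patients section, which requires LVEF of at least 40%, no active ischemia and optimal tolerated therapy, and excludes patients aged 80 or over and those with major systemic illness. Other deaths are not hidden either, since they are recorded by type and total mortality is the secondary endpoint. All of this stands, and it limits the point to an improvement in reporting.

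Censoring of non-MAE deaths is also nowhere written down. That is correct, and it is an inference here. But if those deaths were counted as failures, the curve would no longer show freedom from the primary endpoint as defined. Censoring is therefore the natural reading.

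A reader might infer more than the documents support:
- That the primary test is biased. It is not, as a cause-specific comparison.
- That calling Group 3 an at-risk population rests on an inflated absolute risk. No section says so; the plan sets no risk threshold.
- That Group 3 is the most distorted because it has the most other deaths. Nothing in the documents shows which group has the most. The relative excess depends mainly on the other-death rate, and the excess in points depends on the MAE rate as well.

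**Conclusion.** The point holds as a minor matter of estimation and display. On the natural reading that non-MAE deaths are censored, MAE risk read off the Kaplan-Meier curves is biased upward whenever such deaths occur. The direction is a mathematical result. The size rests on assumed constant rates, because the documents give none.

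At 3 years the likely overstatement is about 0.2-0.7 points, with MAE at 5-10% and other deaths at 1-2% per year. Over the assumed ranges it is at most about 1.8 points, reached with MAE at 10% and other deaths at 5% per year. With a Group 3 of about 37 patients, even that is about a quarter of a standard error. The logrank comparison and the planned sample size are unaffected. The change is worth making because it is cheap, not because a conclusion depends on it.

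**What to change.** State in the Statistics section that nonsudden cardiac and noncardiac deaths are competing events for the MAE endpoint. Then:

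1. Plot and report the Aalen-Johansen cumulative incidence of MAE by group, with non-MAE death as the competing event.
2. Keep the logrank test, described as a comparison of cause-specific MAE hazards.
3. Add one supportive curve by group for MAE or death from any cause. It does not depend on how deaths are classified. That is useful because sudden death is defined by a one-hour window, and any death that is neither sudden nor related to heart failure is noncardiac by default.

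The cost is one estimator replaced and one extra curve, using deaths already collected and classified. The displayed MAE risk will be slightly lower.

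The change does not settle everything about absolute risk. Only Group 3 was offered an ICD, and appropriate ICD activation counts as an MAE, so detection of events still differs between groups whichever estimator is used.

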Study protocol: A two-step stratification algorithm was implemented(1). Upon the first step of the algorithm, an ambulatory 24-hour, as well as signal-averaged electrocardiogram recordings were obtained and evaluated for the presence of the following NIRFs(1, 5-8): (1) >30 premature ventricular complexes/hour on 24-hour electrocardiography, (2) presence of non-sustained ventricular tachycardia on 24-hour electrocardiography, (3) 2/3 positive criteria for late potentials, either conventional or modified(8), (4) QTc derived from 24-hour electrocardiography >440 ms (men) or >450 ms (women)(6) according to the Fridericia formula from a signal recorded in 3 pseudo-orthogonal leads, (5) Ambulatory T-wave alternans $\geq 65\mu$ V in two Holter channels(5), (6) Standard deviation of normal RR intervals ≤ 75 ms on the 24-hour electrocardiography, (7) Deceleration capacity ≤ 4.5 ms and heart rate turbulence onset $\geq 0\%$ and heart rate turbulence slope ≤ 2.5 ms(7).

In the presence of at least one NIRF, patients underwent invasive PVS and were classified as inducible if sustained monomorphic ventricular tachycardia or ventricular flutter or polymorphic ventricular tachycardia were induced. The arrhythmia induced was defined as sustained monomorphic ventricular tachycardia when a uniform morphology of QRS complexes with a rate between 120-220bpm was observed, while persisting for ≥ 30 seconds (or shorter, if termination was necessary due to hemodynamic instability). Faster rates of regular monomorphic ventricular tachycardia (≥ 220 bpm) not permitting QRS complexes to be readily distinguished from T waves and without deterioration towards fibrillation, were defined as ventricular flutter, but they were included in the monomorphic category. Polymorphic ventricular tachycardia was defined if constantly changing morphologies and axis were present, eventually degenerating into fibrillation. See “Appendix” for PVS protocol details.

Patients with paroxysmal atrial fibrillation were evaluated for NIRF presence and submitted to PVS while on sinus, with same stimulation protocol implemented in all cases.

Risk level groups: After completion of the study protocol, patients were stratified into three groups:

- Group 1 – No NIRFs present – no invasive PVS performed
- Group 2 – At least one NIRF present – noninducible upon PVS
- Group 3 – At least one NIRF present AND inducible upon PVS.

An ICD was offered only to Group 3 patients.

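### Device activations count as primary events but only Group 3 was offered an ICD, and no planned analysis separates device-only events, so Group 3's event rate is open to upward bias.

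*Combined protocol and SAP*

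**What the plan says.** - **Goal (Statistics).** To assess whether a "two-step PVS-inclusive risk stratification" algorithm picks out a subpopulation at risk of MAEs.
- **Groups (Risk level groups).** After the protocol, "patients were stratified into three groups": no noninvasive risk factor (NIRF), NIRF but noninducible, NIRF and inducible. "An ICD was offered only to Group 3 patients".
- **Primary endpoint (Outcomes).** MAEs, "namely either SCD/clinical ventricular tachycardia/fibrillation or/and appropriate ICD activation". Total mortality is secondary.
- **Surveillance (Follow up).** Implanted patients are seen every three months, others every six. Device activations are adjudicated by two electrophysiologists, with a third for disagreements.
- **Detection (ICD programming).** VT therapy starts at a cycle length of 330 ms after 32 intervals, or after 7 s in devices programmed by time. Criteria are shorter below 270 ms.
- **Test (Statistics).** For Kaplan-Meier curves, "the logrank test was applied to assess the presence of statistically significant differences". No groups are named. The Power analysis refers to "the null hypothesis that the exposed and control survival curves are equal", but there exposed and control mean low and high SDNN, not risk groups.
- **Declined ICDs (Study protocol).** Patients who refused an offered ICD stay in all analyses, so Group 3 can mix implanted and non-implanted patients.

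**The concern.** One component of the primary endpoint can be recorded only by a device, and under the plan only Group 3 receives one. Some arrhythmias that would be logged, treated and counted in an implanted Group 3 patient could pass unrecorded in Group 1 or 2. Twice-as-frequent visits act in the same direction. Any logrank contrast involving Group 3 then mixes a difference in risk with a difference in detection, and the Statistics section plans nothing to separate them.

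A second, smaller matter is interpretation. With three groups and no named contrast, a significant result could be read as evidence for the invasive step when the difference arises at the noninvasive step. At stake is how much of an observed difference is credited to programmed stimulation, an invasive test that leads to the offer of an implant.

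**Working it through.** **1. The plan's own figure.** 66 × 12 = 792 and 66 + 792 = 858, so the ratio is consistent. The sample size cannot be fully reproduced because no baseline event rate is given. It is built on SDNN with a relative risk of 0.65, so its 80% power does not carry over to any contrast involving Group 3.

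**2. Who can have which event.**

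| Component | Groups 1 and 2 | Group 3, ICD declined | Group 3, implanted |
|---|---|---|---|
| SCD | yes | yes | yes |
| Clinical VT/VF | yes | yes | yes |
| Appropriate activation | no | no | yes |
| Visits | 6-monthly | 6-monthly | 3-monthly |

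**3. Do detection settings close the gap?** From ICD programming:
- 32 × 330 ms = 10.56 s; 32 × 270 ms = 8.64 s; 7 s if programmed by time.
- Fast zone: 18 to 24 intervals at 270 ms = 4.86 to 6.48 s, or 2.5 s by time.

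The only VT duration in the documents is for arrhythmia induced at PVS: at least "30 seconds (or shorter, if termination was necessary due to hemodynamic instability"). Clinical VT in the endpoint has no duration. A tolerated 15 s run at about 182 bpm (60/0.330) or faster could be treated and counted with a device and go unrecorded without one. The NIRF list includes "presence of non-sustained ventricular tachycardia on 24-hour electrocardiography", so such runs are plausible in Groups 2 and 3, though their frequency is unknown.

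**4. Size under assumptions.** Logrank simulation, two-sided 0.05, exponential hazards, follow-up uniform over 2 to 4 years (mean 3, as in the Power analysis), total 858. There are 32 + 5 = 37 documented implants. Groups 2 and 3 have equal true risk, and the observed rate in implanted patients is multiplied by m. The splits, rates and m are assumptions.
- Set A: 550/271/37 and 400/421/37, all Group 3 implanted. Group 1 at 0.5 to 3% per year with a NIRF hazard ratio of 1/0.65 = 1.54, or 0.5 and 1% with a ratio of 3 or 4.
- Set A60: as A, with splits 550/248/60 and 400/398/60, 37 implanted.
- Set B: 708/110/40, 650/160/48 and 550/248/60, 37 implanted, with the same 3-year risk (2% or 5%) in all groups.

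False significance:

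| m | 3 vs 2, A | 3 vs 2, A60 | 3 vs 2, B | 3 vs 1+2, B |
|---|---|---|---|---|
| 1 | 4–5% | 3–6% | 3–4% | 4–5% |
| 1.5 | 10–21% | 6–15% | 6–11% | 8–15% |
| 2 | 18–49% | not run | 12–19% | 15–28% |

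In Set B no group differs in true risk, so the last column shows that detection alone also affects the whole-algorithm contrast.

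**5. The contrast.** With no device effect, Groups 2 and 3 at equal risk and NIRF hazard ratio 1.54, Group 3 vs Groups 1+2 rejects in about 6 to 12% of trials. Group 3 vs Group 2 rejects in 4 to 5% across Set A.

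**6. Precision.** Without inflation, expected Group 3 events in Set A run from 37 × (1 − exp(−3 × 0.005 × 1.54)) = 0.8 to 37 × (1 − exp(−3 × 0.03 × 1.54)) = 4.8. Power of Group 3 vs Group 2 at a true hazard ratio of 2 is 18 to 49%. These are the same runs as the m = 2 row for Set A: this test cannot tell a twofold detection effect from a twofold risk.

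**7. What dropping device-only events does.** Suppose a true hazard ratio of 2, m = 1.5, and half of true events seen only as activations (assumed). Counting everything targets 2 × 1.5 = 3; dropping device-only events targets 2 × 0.5 = 1 and rejects in only 4 to 6% of trials. The second analysis is conservative.

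**The case against.** The strongest reply is that the plan already guards against over-detection. Detection is prolonged to avoid treating runs that would stop by themselves, activations must be appropriate and are adjudicated, and total mortality needs no device. The 30 s criterion describes induced VT, not follow-up events, and a run must be fast, long enough, tolerated and otherwise unnoticed to matter. All of this stands and limits the bias. It does not remove it: adjudication confirms that a recorded activation was appropriate, but cannot recover unrecorded arrhythmia in Groups 1 and 2. Mortality is only partial cover, since an ICD may itself affect it.

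A second reply is that the goal concerns the algorithm as a whole, so Group 3 vs Groups 1+2 is a suitable contrast. That also stands. Group 3 vs Group 2 is needed only for a claim about the PVS step. The cited design paper may name the contrast, so the missing name is by itself a reporting gap.

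A third is that the percentages rest on assumed inputs. That is correct, and they are offered as a range only.

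A reader might go further and infer that significance is close to assured even if inducibility carries no information. A three-group test would reject in 63 to 99.8% of trials under NIRF hazard ratios of 3 to 4. The documents do not support that reading: no section describes a three-group test, those ratios are not in the documents, and since Group 1 would truly differ, such a rejection would be correct for the hypothesis tested.

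**Conclusion.** The point holds as an ascertainment problem. Following the plan as written lets group membership decide who can have a device-recorded primary event, with more frequent visits for implanted patients and no analysis that shows how much of a difference depends on this. The direction is upward for Group 3; the size is unknown. Under an assumed 1.5- to 2-fold detection effect, with Group 3 at about 37 to 60, false significance for Group 3 vs Group 2 is roughly 6 to 49%, against about 3 to 6% without it. The range depends on the assumed rates, splits and multiplier.

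The contrast point is secondary. Group 3 vs Groups 1+2 fits the stated goal but does not by itself support a claim about PVS.

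A reader might infer that a significant result would be a detection artefact, or that inducibility does not identify patients at risk. Neither follows: SCD and clinical VT/VF count in every group, and the documents give no event counts by type. The change should be made; confidence is medium because the magnitude rests on assumptions.

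**What to change.** 1. Tabulate first primary events by group and type: SCD, clinical VT/VF, device activation only. Define the last as an activation without a clinically recognised episode.
2. As a sensitivity analysis, repeat the primary contrast without counting device-only activations, continuing follow-up to the next event. Read it beside total mortality.
3. State that the analyses with and without device-only events are not strict bounds: activations may have averted countable events, and the difference in visit frequency remains in both.
4. Name the groups in the primary logrank, carrying over the cited design paper's contrast if it gives one. Base any claim about the PVS step only on Group 3 vs Group 2, with hazard ratio and 95% CI.

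The cost is SAP wording, one table, one repeat analysis and, if a PVS claim is made, one further two-group comparison. Sorting activations into device-only and clinically recognised may need a look back at records, because the documents do not define clinical VT. The downside is imprecision: Group 3 events will be few, so Group 3 vs Group 2 and the analysis without device-only events will have wide intervals, and the claim for the algorithm or the PVS step may be weaker. No change to device programming or follow-up is proposed.

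### The 80% power stated for the two-step algorithm rests on a low-versus-high SDNN calculation, which itself cannot be reproduced because no event rate is given

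*Combined protocol and SAP*

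**What the plan says.** The Statistics paragraph first states the primary goal, which is to assess whether the two-step algorithm, including programmed ventricular stimulation (PVS), identifies patients at risk of major arrhythmic events. It goes on to say that, for this purpose, "the study was designed to have a statistical power of 80% for detecting free from primary endpoint occurrence survival curve divergence" at the 0.05 level. For the analysis, "Kaplan-Meier curves were used to visualize survival free from primary endpoint occurrence and the logrank test was applied". It does not say which of Groups 1, 2 and 3 are compared.

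The Power analysis paragraph explains that PVS data were scarce, so "it was necessary to use metrics derived from noninvasive indices included in this Study as well", and that "SDNN was found to be the variable that required the largest sample". It lists a two-sided 5% type I error, 80% power, and 12 high-SDNN patients (controls) for each low-SDNN patient (exposed). It adds: "The anticipated accrual/mean follow up intervals were 2 and 3 years, respectively", and "Relative risk (based on SDNN performance) of control subjects relative to exposed subjects was equal to 0.65". From these inputs it concludes that "66 exposed subjects and 792 control subjects would need to be studied to be able to reject with a probability of 80" per cent the null hypothesis of equal curves. Both power statements cite the published design paper, which is not among the documents.

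**The concern.** There are two gaps, and the first matters more.

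First, the 80% is attached to one comparison and calculated for another. Low SDNN is one of the seven risk factors in step one of the algorithm (Study protocol section). The algorithm's own output is a three-group classification that also depends on inducibility at PVS. Power for the one does not carry over to the other.

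Second, the power of a logrank test is driven by the number of events, and no event rate, median or event count is among the inputs from which the sample size is said to follow.

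This is the study's only sample-size justification. A reader who takes it at face value will treat a non-significant algorithm result as coming from a comparison with 80% power, and may read it as evidence of no effect. The documents do not support that reading.

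**Working it through.** **1. What can be reproduced.** 66 × 12 = 792 and 66 + 792 = 858. The split agrees with the stated ratio.

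**2. What cannot.** The inputs (all from the Power analysis paragraph) are two-sided α = 0.05, power 0.80, ratio 12, relative risk 0.65 (control to exposed), accrual 2 years and mean follow-up 3 years. Without an event rate, the total of 858 cannot be derived from them. The only route is backward: find the event proportion at which 66 versus 792 gives 80% power.

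**3. If 0.65 is a hazard ratio.** (1.960 + 0.8416)² = 7.849; (ln 0.65)² = 0.1856; exposed share 1/13.
- Schoenfeld: 7.849 / [(1/13)(12/13) × 0.1856] = 596 events, 69% of 858.
- Freedman, extended to 12:1: 7.849 × (1 + 12 × 0.65)² / [12 × (1 − 0.65)²] = 7.849 × 77.44 / 1.47 = 413 events, 48%.
- Per-arm variance: 1/d₁ + 1/d₀ = 0.1856 / 7.849 = 0.0236, where d₁ and d₀ are the events in each arm. This gives about 484–486 events, 56–57%.
- Simulated logrank test (exponential times, 3 years, 20,000 runs): a control hazard of 0.285 per year gives 503 events and 80.0% power. That is 59% of patients, with a control median of ln 2 / 0.285 = 2.4 years. With 2-year accrual and mean follow-up of 3 years, 504 events give 80.1%.

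The closed formulas disagree because the allocation is so uneven. The documents do not say which method was used, so 59% should be read with the range 48–69%.

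**4. If 0.65 is a ratio of 3-year cumulative risks.**
- Pooled two-proportion formula: solve 1.96√[p̄(1 − p̄)(1/66 + 1/792)] + 0.8416√[p₁(1 − p₁)/66 + p₀(1 − p₀)/792] = p₁ − p₀ with p₀ = 0.65p₁. The solution is p₁ = 0.4915, p₀ = 0.3195. Check: 1.96 × 0.0604 + 0.8416 × 0.0637 = 0.172 = 0.4915 − 0.3195. Overall (0.4915 + 12 × 0.3195)/13 = 33.3%, or 285 events.
- Unpooled variance: 34.6%. With continuity correction: 35.2%.
- Simulated logrank test: 30.5% versus 46.9% gives about 272 events, 32%, and 80% power.

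**5. SDNN power at assumed rates.** The rates below are assumptions, because the documents give none. Events = 858 × (1 − e^(−3r)). Simulated logrank test, 20,000 runs per cell, standard error at most 0.4 points.

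| Assumed overall rate per year | Events | Power, 0.65 as hazard ratio | Power, 0.65 as cumulative risk ratio |
|---|---|---|---|
| 1% | 25 | 14% | 15% |
| 2% | 50 | 20% | 21% |
| 3% | 74 | 25% | 27% |
| 5% | 120 | 34% | 40% |
| 10% | 222 | 51% | 68% |

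**6. The algorithm.** Setting out what is given for each comparison shows why the 80% does not transfer.

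| Input | Low vs high SDNN | Two-step algorithm |
|---|---|---|
| Contrast | Stated | Not stated |
| Effect size | 0.65, type not stated | Not given |
| Group sizes | 66 and 792 | Not given |
| Event rate | Not given | Not given |

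**The case against.** The strongest reply is that the plan is open about what it did. It says that PVS data were scarce, that noninvasive indices were drawn on, and that the sample was set by the most demanding variable. If SDNN needs the largest sample, everything else should be at least as well powered. The disclosure stands. The inference does not: it ranks only the variables that were examined, and no input for the algorithm's contrast is shown from which to tell where it would fall.

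A second reply is that the event rate may be in the cited design paper. That also stands, and it limits the conclusion: an input is missing from these documents, and the stated sample size is neither confirmed nor refuted.

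Three stronger readings are tempting, and none is supported.
- *The 80% is an arithmetic error.* The one step that can be checked, the 12:1 split, is right. Event proportions of 32–59% may look high for patients with preserved ejection fraction and no active ischaemia, but that is a judgement; no figure in the documents settles it. Nor do they say from which endpoint the SDNN relative risk was taken.
- *The study is underpowered for its primary goal.* The percentages in step 5 concern SDNN only and rest on assumed rates. They say nothing about the algorithm.
- *The implant count shows how small Group 3 is.* The ICD programming section says "In 32 cases dual-chamber ICDs were inserted, while in the remaining 5 a single-chamber device was chosen", 37 devices in all. Setting that against 858 mixes an observed count with a planned total. Group 3 also includes patients who declined a device, and patients declining PVS are left out of the survival analyses, so neither the group size nor the number analysed is known.

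**Conclusion.** The point holds as a claim that lacks support. The 80% stated for the primary goal comes from a different comparison, and nothing in the documents establishes it for the algorithm, whose power is unknown.

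For SDNN itself, 80% requires about 59% of patients with an event if 0.65 is a hazard ratio (48–69% across closed formulas), or about 32–35% if it is a cumulative risk ratio. These results assume a two-sided 5% test, and the simulations also assume exponential event times and about 3 years of follow-up. Whether such proportions were expected cannot be judged from the documents.

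This should be fixed, because it changes how a non-significant primary result is read. It does not invalidate the design or the planned test.

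**What to change.** No change in enrolment or follow-up is needed.

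1. Remove the 80% from the sentence on the primary goal. Label 66 + 792 as an SDNN-based calculation that is not a power statement for the two-step algorithm.
2. State the event rate and the endpoint behind 66 + 792, and say whether 0.65 is a hazard ratio or a ratio of cumulative risks. If these cannot be given, withdraw the claim of 80% power at 0.65.
3. Name the group contrast for the algorithm's logrank test, for example Group 3 against Groups 1 and 2 combined. Report its hazard ratio with a 95% confidence interval, using a method suited to few events, such as penalised or profile likelihood. A non-significant result can then be read from the interval, which shows the effects that remain compatible with the data. A power figure calculated afterwards would not show this.

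The cost is a rewording of two paragraphs and one added estimate. The downside is that the stated power becomes less favourable.
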